6.5.1 RESCUE THERAPY

N/A

7 STUDY INTERVENTION/EXPERIMENTAL MANIPULATION DISCONTINUATION AND PARTICIPANT DISCONTINUATION/WITHDRAWAL

7.1 DISCONTINUATION OF STUDY INTERVENTION/EXPERIMENTAL MANIPULATION

When a subject discontinues from the study intervention but not from the study, remaining study procedures will be completed as indicated by the study protocol. If a clinically significant finding is identified (including, but not limited to changes from baseline) after enrollment, the investigator or qualified designee will determine if any change in participant management is needed. Any new clinically relevant finding will be reported as an adverse event (AE).

The data to be collected at the time of study intervention discontinuation will include the following:

- The reason(s) for discontinuing the participant from the intervention, and methods for determining the need to discontinue
- If the participant is due to complete assessments within 2 weeks of being discontinued from the study intervention, those assessments will be administered at the time of discontinuation; if the next scheduled assessments are more than 2 weeks from the discontinuation date, the discontinued participant will wait for the next scheduled assessment. Thereafter, the participant will be included in all future scheduled assessments, even though not participating in the intervention.

7.2 PARTICIPANT DISCONTINUATION/WITHDRAWAL FROM THE STUDY

Participants are free to withdraw from participation in the study at any time upon request.

An investigator may discontinue a participant from the study for the following reasons:

- Significant study intervention non-compliance, unless varying compliance is an aspect of the study objectives
- Lost-to-follow up; unable to contact subject (see **Section 7.3, Lost to Follow-Up**)
- Any event or medical condition or situation occurs such that continued collection of follow-up study data would not be in the best interest of the participant or might require an additional treatment that would confound the interpretation of the study
- The participant meets an exclusion criterion (either newly developed or not previously recognized) that precludes further study participation

The reason for participant discontinuation or withdrawal from the study will be recorded on the Participant Status form. Subjects who sign the informed consent form and are randomized but do not receive the study intervention may be replaced. Subjects who sign the informed consent form, and are randomized and receive the study intervention, and subsequently withdraw, will not be replaced.

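### Section 7.2 lets an investigator end a randomized participant's follow-up for non-compliance or a confounding treatment, which undercuts the as-randomized analysis in Section 9.4.2

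*Combined protocol and SAP*

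**What the plan says.** Section 7.1 covers stopping the intervention only: "When a subject discontinues from the study intervention but not from the study, remaining study procedures will be completed". Such a participant keeps being assessed: "Thereafter, the participant will be included in all future scheduled assessments, even though not participating in the intervention".

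Section 7.2 covers leaving the study: "An investigator may discontinue a participant from the study for the following reasons". Two of its reasons matter here.

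- The first is "Significant study intervention non-compliance, unless varying compliance is an aspect of the study objectives".
- The second is an event or situation that "might require an additional treatment that would confound the interpretation of the study". The same bullet also covers the case where "continued collection of follow-up study data would not be in the best interest of the participant".

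After the list, Section 7.2 deals with recording the reason and with replacement: "Subjects who sign the informed consent form and are randomized but do not receive the study intervention may be replaced". It provides for no further assessments.

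Section 9.4.2 commits to analysing all participants in their randomized arm irrespective of adherence. It uses a linear mixed model for the week 13 and week 25 BPI GPS, with baseline GPS as a covariate. Its sensitivity analyses are inverse probability weighting, with weights derived from baseline characteristics, and models that add indicators of new pain medication and complementary treatment. Section 9.4.9 says that medication use is tracked but not restricted. Section 9.3, although titled as the analysis populations, describes only the recruitment pool.

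**The concern.** An as-randomized analysis depends on outcomes being collected from people who do not adhere or who take up other treatment. Section 7.2 allows follow-up to end for those same two reasons, and no sentence sends such a participant to Section 7.1 or to Section 7.2. Two staff members could follow the protocol faithfully and treat identical participants differently, one keeping the week 25 BPI and the other losing it.

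The loss would not be random. It would depend on behaviour after randomization, and that could differ by arm: web-based CBT exists in two arms and motivational interviewing calls in one. If poorly adhering participants also do worse, removing more of them from one side makes that side look better. The sensitivity analysis on new pain medication has a similar problem, since it can use only participants who still have an outcome after the added treatment.

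**Working it through.** **1. Does leaving under Section 7.2 end outcome collection?** The text does not say so outright. Section 7.1 ties continued assessment to remaining in the study, one Section 7.2 reason is framed as ending data collection, and Section 7.2 arranges no later visits. The inference is sound, but it is an inference.

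**2. What does the primary model lose?** Baseline GPS is a covariate, so the only outcome rows are weeks 13 and 25.
- Removed before week 13: no rows, so no contribution to the primary analysis.
- Removed after week 13: the week 13 row stays, and the model borrows from it.

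**3. Does the weighting repair it?** Weights from baseline characteristics can correct loss that those characteristics explain. Removal for later non-compliance is not of that kind. In 10,000 simulated trials (single follow-up ANCOVA, the 15% v 5% removals of step 5), the shift was -0.099 unweighted and -0.099 weighted.

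**4. The plan's own figures (Section 9.2).** SD = 2.2 × √(1 - 0.5²) = 1.905, stated as about 1.9. Evaluable per arm = 280 × 0.8 / 3 = 74.7, stated as 75. Noncentral t power for a 1-point difference, two-sided alpha 0.025, SD 1.9:
- Aim 2 (75 v 75): 83.0%, stated 83%.
- Aim 1 (150 v 75): 92.8%, stated 90%, so the plan is conservative.

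**5. Size of a possible shift (illustration; every removal input is assumed).** Suppose there is no true effect, and 20% of each arm are non-compliers who score 1 point worse. If a fraction r of an arm is removed, all of them non-compliers, the excess left in the arm mean is (0.20 - r)/(1 - r).
- 15% removed in the combination arms, 5% in monotherapy: 0.0588 - 0.1579 = -0.099.
- 20% v 0% (the extreme in this scenario): 0 - 0.200 = -0.200.
- 10% v 10%: 0.
- Reversing the arms reverses the sign.

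These apply when all removals come before week 13. Timing was checked by simulating the two-visit model (4,000 trials per scenario, arms of 94/93/93, baseline correlation 0.5, assumed correlation of 0.7 between weeks 13 and 25, 20% ignorable loss with half before week 13; Monte Carlo SE 0.004). Mean H1 shift:

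| Removed, combination v monotherapy | Before week 13 | After week 13 |
|---|---|---|
| 15% v 5% | -0.105 | -0.018 |
| 20% v 0% | -0.196 | -0.043 |
| 10% v 10% | -0.002 | +0.006 |

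With outcomes still collected, the shift is 0.000.

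**6. Effect on type I error for H1.** SE = 1.905 × √(1/150 + 1/75) = 0.2694. The rejection probability for a shift b is Φ(-2.241 + b/SE) + Φ(-2.241 - b/SE).
- b = 0.02: 2.54%.
- b = 0.04: 2.66%.
- b = 0.10: 3.5%.
- b = 0.20: 6.8%.

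The first two correspond to removal after week 13. The last two need removal that is early, confined to non-compliers and clearly unbalanced.

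**7. Power.** This changes only if removals come on top of the planned 20% loss, which is an assumption. At 25% total loss, n per arm = 280 × 0.75 / 3 = 70. With the stated SD of 1.9, Aim 2 power is 80.1% and Aim 1 power 90.9%.

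**The case against.** The best case for the plan is that the text is looser than ideal but does no harm.

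- **The power is discretionary, and there is no contradiction.** A reader might infer that Section 7.2 contradicts Section 7.1 or 9.4.2. It does not. Section 7.1 is limited to people who remain in the study, and a plan can analyse as randomized while permitting withdrawals. This stands. What remains is the missing routing rule.
- **The non-compliance reason limits itself.** Its qualifier plausibly exempts coping-skills practice, which is the subject of Aim 2 and an exploratory outcome. What would then remain is mainly duloxetine compliance, common to all arms. This is a fair reading, but the protocol does not state it. The confounding-treatment reason carries no such qualifier.
- **Early removal may be uncommon.** Participants take duloxetine for a week before randomization at week 1, so some early intolerance leaves beforehand. In Table 1 the next drug accountability entry appears to fall near week 13, although the column alignment is uncertain. This narrows the problem. It does not close it, because symptom contacts at weeks 2 and 4 and weekly reports of missed support calls (Section 8.2) can reveal non-compliance sooner.
- **Blinding.** Section 6.3 blinds the PI, which helps. Section 7.2 gives the power to an investigator, who need not be the PI.
- **Newly met exclusion criteria.** A reader might see a clash between "The participant meets an exclusion criterion (either newly developed or not previously recognized) that precludes further study participation" and the rule in Section 8.2 that pregnant participants stay in the study. There is none: the reason covers only criteria that preclude further participation, and Sections 2.3.1 and 8.2 both keep these participants in.
- **Retention detail** is deferred to the Manual of Procedures, which is not among the documents. It may settle the routing, but the protocol should not depend on that.

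**Conclusion.** The concern holds as a gap that should be fixed. A stated permission, followed as written, can remove outcomes that Section 9.4.2 relies on, for reasons that Section 9.4.2 says should not matter, and the planned weighting would not recover them.

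The size and direction of any bias are unknown because the documents give no removal rate. It is negligible if removals are balanced or come after week 13 (type I error about 2.5% to 2.7%). A reader might take the 3.5% or 6.8% in the working as the expected inflation. The documents do not support that: the share of non-compliers, their 1-point disadvantage, the imbalance and the timing are all assumed.

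Nor do the documents support saying that Aim 2 power falls below 80% at 25% loss. It is 80.1% with the stated SD of 1.9, and slips to 79.8% only with the unrounded 1.905. That removals would add to the planned 20% loss is itself an assumption.

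**What to change.** Limit the change to data collection and analysis, and leave every treatment decision as it is.

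1. In Section 7.2, state that non-compliance or additional treatment does not by itself end outcome collection. Such participants follow the Section 7.1 assessment path, with the week 13 and week 25 BPI collected unless consent is withdrawn or further data collection is not in the participant's interest. Section 4.4 already treats having the week 25 BPI GPS as separate from completing the arm's activities, so this fits the existing definitions. It also means that the scope of the compliance qualifier no longer decides whether outcomes are collected.
2. In Section 9.3 or 9.4.2, state that a randomized participant who is replaced under Section 7.2 stays in the as-randomized analysis, and that the replacement is additional.

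The cost is a few sentences and a few more follow-up contacts with people who are off treatment. Their outcomes will enter the estimate, as Section 9.4.2 already intends.

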7.3 LOST TO FOLLOW-UP

A participant will be considered lost to follow-up if he or she fails to return for one IPV and study staff are unable to contact the participant after at least 3 attempts.

The following actions must be taken if a participant fails to return to the clinic for a required study visit:

- The staff will attempt to contact the participant, reschedule the missed visit, counsel the participant on the importance of maintaining the assigned visit schedule and ascertain if the participant wishes to and/or should continue in the study.
- Study staff will utilize a participant provided alternate contact list, if necessary, to reach the participant.
- Before a participant is deemed lost to follow-up, the investigator or designee will make every effort to regain contact with the participant (where possible, 3 telephone calls and, if necessary, a certified letter to the participant's last known mailing address or local equivalent methods). These contact attempts will be documented in the participant's medical record or study file.
- We will use multiple methods to contact participants who drop out, including text messaging and/or email.
- Should the participant continue to be unreachable, he or she will be considered to have withdrawn from the study with a primary reason of lost to follow-up.

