sessions, which we have found users prefer). Session 1 starts with an overview of the CBT program, and the intervention's therapeutic rationale. This overview is followed by training in the first pain coping skill: progressive muscle relaxation. Sessions 2-7 teach, respectively, brief relaxation skills (i.e., "mini-practices"), activity-rest cycling, pleasant activity scheduling, cognitive restructuring ("coping thoughts"), pleasant imagery, and problem solving. Session 8 reviews each skill to consolidate learning and teaches strategies for long-term skill use. Between sessions, participants are asked to practice their newly learned skill and any skills they learned in past sessions. The program also includes a feature to enhance engagement and facilitate practice. This feature is a section of the program that participants access to self-monitor their progress by reviewing and changing practice goals, recording practices and "coping confidence" (self-efficacy for managing pain), viewing graphic summaries of progress over time, and managing automated practice reminders.

Health care professional-delivered MI. The primary purpose of health care professional contact is to enhance participant's motivation to engage in web-based CBT by encouraging participant's continued use and practice of pain coping skills. Subjects randomized to the [duloxetine + web-based CBT] with health care professional support will receive 6 phone calls from MI trained health care professional at week 3, 6, 10, 14, 18 and 22. Telephone sessions may run for 20 minutes on the average. Similar to our previously tested MI protocol to encourage exercise, the MI intervention has 3 phases:

1. First phase: The first two calls will focus on strategies that enhance motivation to practice newly learned pain coping skills. It involves eliciting from the patient statements (i.e. self-motivational statements) that support the following: a) The patient's recognition of the full nature and extent of the problem, b) The patient's concern about how he or she is currently managing the problem, c) The patient's intention of changing in the direction of adaptive pain management, and d) The patient's optimism that changes are possible.

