10.2 ADDITIONAL CONSIDERATIONS

In case of **complete** shutdown of all clinical research activities,

1. Participants will complete the questionnaires online.
2. We will mail the medication (and urine pregnancy test if relevant) to the participant's home address. Participant will take a picture of the result of the pregnancy test and email it to the research staff.

In case of **partial** shutdown of all clinical research activities,

1. Participants will complete the questionnaires online.
3. Participants will pick up the medication (and urine pregnancy test if relevant) on a designated pick up area within the medical center. Participant will take a picture of the result of the pregnancy test and email it to the research staff.

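### Section 7.3 can close a participant's follow-up after one missed visit at Week 13, with no instruction to attempt the Week 25 primary outcome anyway

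*Combined protocol and SAP*

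**What the plan says.** Section 7.3 opens with this rule: "A participant will be considered lost to follow-up if he or she fails to return for one IPV". A second condition applies with it: three or more tries at contact must have failed. Before that label is applied, staff are to try to reschedule the visit, use the alternate contacts that the participant supplied, telephone, and if necessary send a certified letter. It adds: "We will use multiple methods to contact participants who drop out, including text messaging and/or email". The section then concludes: "Should the participant continue to be unreachable, he or she will be considered to have withdrawn from the study". It sets no time limit, has no re-entry rule and does not mention Week 25.

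Four other places bear on this:

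- Section 7.2 is permissive. It introduces its list, which includes loss to follow-up, with: "An investigator may discontinue a participant from the study for the following reasons".
- Section 4.4 counts data as complete when the Week 25 BPI-GPS is collected. Week 13 attendance is not part of that definition.
- Section 7.1 keeps a participant who stops the intervention in every later scheduled assessment.
- Section 10.2 provides an online route ("Participants will complete the questionnaires online"), but only for a complete or partial shutdown of clinical research.

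Section 9.4.2 takes BPI GPS at Weeks 13 and 25 as the primary outcome. It fits a linear mixed model with baseline BPI as a covariate and analyses everyone as randomized.

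**The concern.** After Week 1 there are only two in-person visits, Weeks 13 and 25. Week 13 is therefore the one visit after the start of treatment at which the 7.3 rule can cost a later primary outcome. A missed Week 13 visit need not be the end of a participant's data. The person may resurface, and a Week 25 score alone would satisfy Section 4.4 and enter the primary model. If staff read the withdrawn status as closing the case, that score is never sought.

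Baseline is a covariate and not a repeated outcome, so a participant with neither follow-up score drops out of the primary analysis altogether. At stake are the completeness of the primary outcome for both hypotheses and the intention to analyse all randomized participants. The planned inverse-probability-weighting sensitivity analysis builds its weights from baseline characteristics. It can reweight the people who were observed, but it cannot replace scores that nobody tried to collect.

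**Working it through.** **1. The provisions side by side**

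| Situation | Section | Week 25 attempted? |
|---|---|---|
| Stops the intervention, stays in contact | 7.1 | Yes, explicitly |
| Misses Week 13, is reached and rescheduled | 7.3 | Yes, by implication |
| Misses Week 13, stays unreachable after the outreach | 7.3 | Treated as withdrawn; no instruction |
| Has a Week 25 score but no Week 13 score | 4.4 and 9.4.2 | Counts as complete; usable in the model |

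The third row is the problem. The gap between the two visits is 25 − 13 = 12 weeks.

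**2. The plan's own planning figures** (Section 9.2: 280 participants, 20% loss, SD 1.9, difference 1, two-sided alpha 0.025)

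- Allowed loss: 0.20 × 280 = 56.
- Evaluable: 280 − 56 = 224, and 224 / 3 = 74.7 per arm. The stated 75 reproduces.
- Aim 2 standard error: 1.9 × √(2/75) = 0.31. Power from the noncentral t distribution is 83.0%, so the stated 83% reproduces.
- Aim 1 (150 vs 75): 92.8% by the same method against a stated 90%. The stated figure is conservative, and this is not part of the present point.

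**3. Cost per 5% closed out at Week 13**

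0.05 × 280 = 14 Week 25 scores, and 14 / 56 = 25% of the whole loss allowance. This is an upper bound. Some of these people would have been missing at Week 25 in any case, and the 20% already covers loss from every cause.

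**4. If such losses came wholly on top of the 20%** (an assumption; the documents give no rate)

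| Total loss | n per arm | Aim 1 power | Aim 2 power |
|---|---|---|---|
| 20% | 74.7 | 92.7% | 82.8% |
| 25% | 70.0 | 90.9% | 80.1% |
| 30% | 65.3 | 88.7% | 77.0% |

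**5. If loss also differed by arm** (assumed rates; simple contrast of observed means)

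The observed mean in an arm is too favourable by (proportion lost) × (how much worse the missing participants would have scored). The shift in the H2 contrast is therefore (loss without support − loss with support) × gap.

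- 20% vs 15%, 1-point gap: 0.05 × 1 = 0.05. With a 2-point gap: 0.10.
- 25% vs 10%, 1-point gap: 0.15 × 1 = 0.15. With a 2-point gap: 0.30.

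These shifts understate the benefit of support. If the supported arm lost more, the sign reverses. For scale, the design difference is 1 point and the Aim 2 standard error is 0.31.

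**The case against.** The strongest reply is that a missed visit alone triggers nothing. Withdrawn status follows only after rescheduling attempts, calls, alternate contacts, possibly a certified letter, and text or email, with the same steps in every arm. Section 7.2 leaves discontinuation to the investigator's discretion. Section 7.3 speaks of contacting people who have already dropped out, and nothing bars someone who reappears. Table 1 includes a missed-visit form, and Section 5.5 refers retention detail to a manual that is not among these documents. On this view the data are lost because the person cannot be found, and the label only records it.

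Much of that stands. No passage says that Week 25 collection stops, so the finding is that the rule can close follow-up, not that it must. But the closing sentence of 7.3 is not discretionary in the way 7.2 is, so staff have two readings and no Week 25 instruction. Being unreachable around Week 13 does not mean being unreachable 12 weeks later.

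A reader might go further and infer that the rule biases the comparison between arms, because only the supported arm "will receive 6 phone calls from MI trained health care professional at week 3, 6, 10, 14, 18 and 22". Three of those calls fall after Week 13, while the symptom-monitoring contacts planned for all arms are at Weeks 1, 2, 4, 13 and 25. The documents do not support that inference:

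- The calls are motivational sessions. Nothing says that they serve for tracing or continue once someone is classed as withdrawn.
- Text appointment reminders are allowed for participants in all arms, and both combination arms have automated practice reminders.
- The amendment history (version 6) records that a substantial share of participants found study calls burdensome and did not answer or return them. Extra calls could therefore hurt retention as easily as help it.

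**Conclusion.** The concern holds as a defect in the follow-up rule. Section 7.3 can turn one missed visit into withdrawal before the assessment that defines complete data. It does not say that Week 25 will still be attempted, and it sits poorly with Sections 4.4 and 7.1. The loss is at most 14 Week 25 scores per 5% of participants closed out. The true number cannot be stated because no Week 13 miss rate is given. If total loss reached 25% to 30%, Aim 2 power would be about 80% to 77%, so the harm is moderate and not fatal to the design.

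Differential loss between arms remains possible but unproven in size and direction. The shifts of 0.05 to 0.30 point rest entirely on assumed rates and gaps and should not be read as an estimate of bias. No change to the sample size or the primary model follows.

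**What to change.** Amend Section 7.3 along these lines:

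- A missed Week 13 visit is recorded as a missed visit and does not change study status.
- The Week 25 BPI is attempted in every randomized participant who has not withdrawn consent, with the same Week 25 tracing steps in all three arms.
- Lost-to-follow-up status is assigned only when the Week 25 window closes. The protocol text states no visit window, so it should give one or cite where it is defined.
- Participants who can be reached but cannot attend may complete the BPI by the online route in Section 10.2, with the mode of completion recorded.

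Bring the loss-to-follow-up item in Section 7.2 into line with this.

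The change should not add contacts between visits. Professional contact is what H2 tests, so an equalized call schedule would alter the comparison. Online completion will not recover people who cannot be reached. It helps those who are found again but cannot come in.

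The cost is protocol wording, a few extra contact attempts around Week 25 and a minor mix of completion modes.
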